9.2.3.1 Protocol defined SAEs

CM is a disease with a high mortality rate. Reported mortality rates range from 15 – 30%, with our site having a rate of 18% over the past 25 years. We anticipate the mortality rate in randomization arm 3 will be approximately 37%. All deaths not attributable to the malarial illness will be reported to independent safety monitors, IRBs, and the sponsor as required.

- Death not caused by respiratory arrest secondary to intracranial hypertension.
- Prolongation of existing hospitalization for more than 7 days due to an intervention.
- A life-threatening adverse event that is not part of the study outcomes defined in the study objectives, an attributable to an intervention.

9.2.4 Procedures to be Followed in the Event of Abnormal Laboratory Test Values or Abnormal Clinical Findings

9.2.4.1 Hypernatremia

Table 3 (Section 6.1.5) categorizes the possible serum sodium levels and actions to be taken if they are observed. A serum sodium measurement of greater than 190 mmol/L will be considered an SAE and reported as such. The 3% HPS infusion will be stopped. Maintenance fluid infusion will continue at maintenance rate. Sodium will be rechecked hourly until its serum level is < 160 mmol/L and therapy will be resumed as per Table 3.

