2.1.12 Quantitative vascular physiology measurements

Transcranial Doppler Ultrasound (TCD)

Transcranial Doppler Ultrasound (TCD) is a portable, non-invasive, easy to use tool that quantifies cerebral blood flow velocities (CBFV)⁷². TCD has been widely used to assess cerebrovascular physiology in number of neurologic illnesses in children⁷³⁻⁷⁵. Specific alterations to TCD derived flow velocities and waveform morphologies enable characterization of specific pathologic changes to the neurovasculature during illness. In 160 children with retinopathy positive cerebral malaria, five distinct changes to expected flow velocity patterns were noted (Figure 5).⁷⁶

[figure not shown]

Figure 5. A. Normal middle cerebral artery (MCA) transcranial Doppler ultrasound (TCD) flow velocities and waveform for a 3-year-old child. Peak= systolic, EDV= end diastolic velocity, PI= pulsatility index . TCD with normal systolic flow velocity, reduced diastolic flow velocity, increased pulsatility index. These findings represent a child categorized as having microvascular obstruction. C. TCD with increased systolic flow velocity, increased diastolic flow velocity, loss of dichrotic notch. Lindegaard ratio (LR) <3 . These findings represent a child categorized as having hyperemia. D. TCD with increased systolic flow velocity, increased diastolic flow velocity, presence of dichrotic notch. LR >3 . These findings represent a child categorized as having cerebral vasospasm. E. TCD with decreased systolic flow velocity, decreased diastolic flow velocity, decreased mean flow velocity. These findings represent a child categorized as having low flow. F. TCD with increased systolic flow velocity, increased diastolic flow velocity, increased mean flow velocity in the basilar artery. At the same time, all measurements in the middle cerebral arteries were normal. These findings represent a child categorized as having isolated posterior hyperemia.

Each flow velocity phenotype was identified with different frequency (microvascular obstruction 22%, hyperemia 26%, vasospasm 13%, low flow 26%, isolated posterior hyperemia 4%) and was associated with different neurologic outcomes. Children found to have low flow were most

likely to die (Table 3). Children diagnosed with vasospasm were most likely to survive, but with neurologic sequelae.

Table 3: Predicted probabilities (with 95% confidence intervals) of neurologic sequelae or death in children with cerebral malaria in each TCD diagnostic group.

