6.3 Modification of Study Intervention for a Participant (HPS)

Although sodium abnormalities are rare in CM, in the event that a participant has a (Na⁺) level of > 150 mmol/L on admission, the initial bolus will be deferred and the sliding scale dosing detailed in Table 3 will instead be followed.

The subsequent dosing of HPS is planned on a sliding scale, with the goal of maintaining serum sodium levels between 150 and 160 mmol/L. Serum sodium levels will be checked every 3 hours for the first 12 hours of the study, and then every six hours, unless designated otherwise (Table 3).

Table 5. Dosing schedule for hypertonic saline

Serum Sodium	Dose of 3% HPS	Sodium recheck
< 145 mmol/L	5 mL/kg (bolus)*	3 hours
145 – 150 mmol/L	2 mL/kg (bolus)*	3 hours
150 - 160 mmol/L	None	6 hours
>160 mmol/L	Hold infusion until serum sodium is ≤ 155, restart at 0.5 mL/kg/hr	1 hour

*If > 3 boluses are required to maintain serum sodium between 150-160, then increase infusion by 0.25 mL/kg until no further boluses are required.

Further modifications to the HPS dose will be made in the event of the following laboratory abnormalities (electrolyte abnormality grading detailed in Appendix B):

- Grade 4 hypokalemia (see Toxicity Table in Appendix B)
- A pH drop of more than 0.2 within 6 hours
- Chloride > 125 mmol/L
- Serum osmolality > 340 mOsm

In these instances, planned HPS doses will be held, and corrective actions (detailed in Section 9.2.4) will be taken. Electrolytes will be rechecked in 3 hours and the normal dosing schedule will be reinstated if electrolytes are no longer in the Grade 4 toxicity range.

If the pH < 7.25 or falls by 0.2 within 6 hours or if the serum chloride is > 125 mmol/L, the 3% saline infusion will be stopped and converted to a 1:1 ratio of 3% sodium chloride/sodium acetate solution.

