9.2.1.3 Expected Adverse Events

All adverse events meeting the criteria listed above will be collected. Special concern will be paid to the following adverse events as they are known side effect of the investigational drugs:

- Potentially attributable to the hypertonic saline intervention:
 - Hypernatremia
 - Hypokalemia
 - Hyperkalemia
 - Phlebitis
- Potentially attributable to the intubation intervention:
 - Pneumothorax
 - Pneumomediastinum
 - Subglottic stenosis
 - Stridor
 - Tracheostomy
 - Bronchospasm
 - Pulmonary hemorrhage

- Respiratory nosocomial infections
- Hypotension
- Endotracheal tube obstruction
- Inadvertent endotracheal tube dislodgment
- Bradycardia induced by vagal response

Adverse Event grading tables (attached as Appendix B) will be used to define these conditions. These events will be captured in the CRF and subsequently in tabular format, listing time of event onset, time of event resolution, brief description of the event, clinician's assessment of severity, and clinician's assessment of relation to the intervention. They will be reported to the local ISM on a monthly basis, and an annual report of these events will be presented to the DSMB, as well as both IRBs. The events will be captured for the duration of the participants' stay on the PICU/PRW, independent of whether the participant is still receiving interventional therapy.

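### The serum sodium rules for the hypertonic saline arm do not agree across Table 5, Section 9.2.4.1 and Appendix B

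*Combined protocol and SAP*

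**What the plan says.** Three places in the protocol attach actions or labels to serum sodium in the HPS arm.

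- **Section 6.3** titrates HPS "with the goal of maintaining serum sodium levels between 150 and 160 mmol/L". Its schedule is headed "Table 5. Dosing schedule for hypertonic saline". The 145–150 row gives a 2 mL/kg bolus and a 3-hour recheck. The 150–160 row gives no dose and a 6-hour recheck. The row above 160 reads "Hold infusion until serum sodium is ≤ 155, restart at 0.5 mL/kg/hr", with a 1-hour recheck.
- **Section 9.2.4.1** opens with "Table 3 (Section 6.1.5) categorizes the possible serum sodium levels and actions to be taken if they are observed". It then states "A serum sodium measurement of greater than 190 mmol/L will be considered an SAE and reported as such", stops the infusion, and continues: "Sodium will be rechecked hourly until its serum level is < 160 mmol/L and therapy will be resumed as per Table 3".
- **Appendix B** grades hypernatremia as Grade 1 at 166–170, Grade 2 at 171–180, Grade 3 at 181–190 and Grade 4 above 191 mEq/L. Section 9.2.1.3 lists hypernatremia as an event of special concern for HPS and says "Adverse Event grading tables (attached as Appendix B) will be used to define these conditions". Section 9.2.1.1 also names Appendix B as the grading source for electrolyte abnormalities.

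**The concern.** HPS is titrated directly on sodium in comatose children, so each reading ought to lead to one action, one condition for restarting after a hold, and at most one grade. As written, some readings meet two rules and others meet none.

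Two things are at stake. The first is consistent delivery of the intervention: two clinicians following the text could act differently on the same value. The second is the safety record. The events defined through Appendix B are the ones that Section 9.2.1.3 sends to the independent safety monitor monthly and to the DSMB and both IRBs annually. Safety of HPS is also a secondary objective (Section 3.1).

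**Working it through.** The plan gives no figure to reproduce. The check lays the stated limits side by side and reads off, for whole-number values from 140 to 199, where rules overlap or leave a gap. Sodium is monovalent, so the mEq/L of Appendix B equals the mmol/L used elsewhere.

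| Sodium (mmol/L) | Table 5, Section 6.3 | Section 9.2.4.1 | Appendix B |
|---|---|---|---|
| 150 | two rows: 2 mL/kg bolus, 3 h; and no dose, 6 h | – | no grade |
| 156–159, falling after a hold | hold continues until ≤155 | below 160: hourly rechecks end, therapy resumes by table reference | no grade |
| 161–165 | hold, 1 h recheck | not an SAE | no grade |
| 166–190 | hold, 1 h recheck | not an SAE | Grades 1–3 |
| 191 | hold, 1 h recheck | SAE (above 190) | no grade: Grade 3 ends at 190, Grade 4 is above 191 |
| 192 and above | hold, 1 h recheck | SAE | Grade 4 |

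**1. The value 150.** Both rows print 150 as an endpoint, and nothing marks either as exclusive. The surrounding text does not break the tie. The stated goal puts 150 inside the target, whereas the admission rule in Section 6.3 defers the initial bolus only strictly above 150, which groups 150 with lower values.

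**2. Resuming after a hold.** Values below 160 but above 155 are 156, 157, 158 and 159. The scope of Section 9.2.4.1 can be read in three ways:

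- If it covers all hypernatremia and sets its own restart level, 156–159 has two rules.
- If it covers only readings above 190 and sets its own restart level, a child who reached 191 may resume below 160, while a child who reached 161 waits for 155 or lower.
- If it only sends the reader back to the dosing schedule, a held child at 158 fits both the 150–160 row (6-hour recheck) and the unfinished hold from the row above 160 (1-hour recheck).

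The reference cannot settle this as printed. The only table in the protocol labelled Table 3 is "Table 3: Predicted probabilities (with 95% confidence intervals) of neurologic sequelae or death", the TCD table in Section 2.1.12. The dosing schedule is Table 5 in Section 6.3, and Section 6.1 of the body stops at 6.1.3, so there is no Section 6.1.5. Section 6.3 itself also calls its own schedule Table 3.

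**3. The top of the scale.** The SAE limit is above 190 and Grade 4 is above 191. In whole numbers the gap is the single value 191. On a continuous scale it runs from just above 190 up to and including 191. Section 9.2.1 requires every adverse event to be graded.

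**4. The band above target.** Values above 160 and below 166 are 161–165, which is 165 − 161 + 1 = 5 values. The largest is 165 − 160 = 5 mmol/L above the target ceiling. These readings trigger a hold but fall outside the table that defines the event.

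**Count.** Values without one clear rule or grade: 1 (150) + 4 (156–159) + 1 (191) = 6. Values whose ungraded status is unexplained: 5.

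**The case against.** The strongest case on the other side is that these are drafting slips of unequal weight, and parts of it stand.

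- **Resumption.** Because Section 6.3 also miscalls its schedule Table 3, Section 9.2.4.1 can fairly be read as deferring to that schedule. Below 160 would then end the hourly rechecks only, and 155 would remain the restart level. This softens the conflict from a contradiction to an ambiguity. It does not remove it, since the recheck interval for a held child at 156–159 stays unclear and the reference is still wrong.
- **161–165.** A limit for holding a dose and a limit for grading an event serve different purposes and need not coincide. Section 2.4.1.2 says raised sodium is itself the aim of the treatment, so a margin above target is coherent. This stands: the band is a query, not a contradiction.
- **191.** The infusion is stopped and the SAE reported whatever the grade. This also stands, and the effect is confined to the grade label.

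A reader might also go further than the documents allow:

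- One might infer that bedside staff do receive conflicting instructions. Section 6.2 assigns dosage and rate adjustment to Standard Operating Procedures that are not in the documents, so this cannot be judged. Equally, those procedures do not correct the protocol text.
- One might infer that 150 will be a common reading because it is the lower edge of the target. No sodium distribution is given.
- One might infer that overshoots to 161–165 will be lost. Sodium is measured serially in this arm, so the data will exist. What is uncertain is whether they appear in the adverse-event reports. The halting rule in Section 9.5 on failure to reach the target range may not catch a transient overshoot.
- One might infer that the SAE limit contradicts the hold above 160. One is a reporting rule and the other a dosing rule, so they do not conflict.

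**Conclusion.** The sodium rules for the HPS arm are internally inconsistent in three places: the double entry at 150, the ambiguous rule for 156–159 with its wrong table reference, and the mismatch that leaves 191 an SAE without a grade. The ungraded band 161–165 is a separate, open question, because it may be a deliberate margin that nobody has written down.

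The size is modest. Six whole-number values need one rule or one grade and five need a statement of intent. The point concerns delivery and safety reporting in one arm. Nothing here bears on the primary endpoint, the sample size or the sequential test. It is still worth correcting, because these are operative rules for a titrated infusion and the correction costs little.

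The conclusion assumes readings in whole numbers and that the protocol text governs where the unseen procedures are silent. How often any of these values will occur cannot be estimated from the documents.

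**What to change.** Reconcile Section 6.3 (Table 5), Section 9.2.4.1 and Appendix B so that each sodium value maps to one action, one condition for resuming after a hold, and at most one grade:

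1. Make the Table 5 rows mutually exclusive at 150.
2. State one resume criterion and one recheck interval after a hold, and say whether Section 9.2.4.1 covers all hypernatremia or only readings in the SAE range.
3. Make the SAE limit and the Grade 4 limit agree, with no gap above Grade 3.
4. Replace the references to Table 3 and Section 6.1.5 with Table 5 and Section 6.3, including those within Section 6.3.
5. State whether 161–165 is intentionally ungraded.
6. Whatever the answer, add a safety table of HPS readings above 160 mmol/L (children affected, number of readings, highest value), so that overshoots appear in the HPS safety assessment.

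Which thresholds to adopt is a clinical decision for the investigators and the sponsor. The Standard Operating Procedures should be checked against the reconciled text. The cost is protocol and appendix wording plus one table from electrolytes already collected. No new measurement is needed.

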9.2.4.2 Hypokalemia

As per the toxicity table attached as Appendix B, a serum potassium measurement of <2.0 mmol/L will be defined as a Grade 4 adverse event. Corrective action will be in the form of adding 40 mmol/L of KCl to the maintenance IV fluids (an increase from the 17mmol/L K⁺ present in ½ Strength Darrow’s). IV fluid infusion rate will remain the same. HPS boluses will continue, and electrolytes will be monitored at 3 hour intervals until K⁺ returns to below Grade 3 disturbances.

9.2.4.3 Phlebitis

3% hypertonic saline when administered through peripheral veins over prolonged periods of time may lead to phlebitis. If phlebitis or swelling of the IV catheter site is noted, the IV cannula will be removed and an alternate placed.

9.3 Reporting Procedures

9.3.1 Serious Adverse Events

The reporting period for SAEs will be between the time of randomization and the twelve month (± 2 weeks) post-randomization follow up visit.

SAE reporting will be carried out as follows

The study clinician will complete a Serious Adverse Event Form (Appendix D) and SAEs thought to be related to study related procedures will be reported within 24 hours of their recognition, to the independent safety monitor, the IRBs at Michigan State University and the University of Malawi College of Medicine, and the sponsor, unless advised otherwise by the DSMB.

Any AE that meets a protocol-defined serious criterion will be submitted on an SAE form to the DMID Pharmacovigilance Group, at the following address:

DMID Pharmacovigilance Group
Clinical Research Operations and Management Support (CROMS)
[name]
[name]
SAE Hot Line: [name] (US) or [name] (outside US)
SAE FAX [contact] (US) or [name] (outside US)
SAE Email Address: [contact]

Other supporting documentation of the event may be requested by the DMID Pharmacovigilance Group and will be provided as soon as possible.

The DMID medical monitor and clinical protocol manager will be notified of the SAE by the DMID Pharmacovigilance Group. The DMID medical monitor will review and assess the SAE for regulatory reporting and potential impact on study subject safety and protocol conduct.

At any time after completion of the study, if the investigator becomes aware of an SAE that is suspected to be related to study product, the investigator will report the event to the DMID Pharmacovigilance Group, the independent safety monitor, and the IRBs of the University of Malawi and Michigan State University.

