By focusing on children with CM who have severely increased brain volume per MRI, the study population represents those at highest risk of dying of CM. The mortality rate of retinopathy-positive children with severely increased brain volume is 37%.

Prior to study commencement and based on recruitment patterns over the previous five years (the years that the MRI has been available for characterizing brain volume) we expected to enroll approximately 30-35 retinopathy-positive and 10-12 retinopathy-negative participants with severely increased brain volume per year.

The rate of participant enrollments has decreased, and challenges have been faced in almost all study years:

- 2017: the pediatric intensive care unit remained under construction. Given a steady decline in enrollment rates for pediatric cerebral malaria on the Research Ward, a referral network of 6 hospitals within an hours' drive of the Queen Elizabeth Central Hospital was established. No participants were recruited or randomized.
- 2018: The Malawi Pharmacy, Medicines and Poisons Board unexpectedly delayed the clearance needed to import 3% hypertonic saline (HPS). Protocol amendments were made quickly. Fifty-seven participants were recruited, and 8 were randomized: 4 to usual care and 4 to ventilatory support.
- 2019: The inability to import 3% HPS to Malawi continued. A total of 42 participants were screened, and 24 were randomized (12 to ventilatory support and 12 to usual care).
- 2020: The MRI scanner became non-functional and repair efforts were stymied by the adverse impact of the COVID-19 pandemic on international travel. (The repair technician could not travel from South Africa to Malawi after all commercial flights to Malawi ceased.) A total of 48 patients was screened, but none were randomized because brain volume could not be assessed. We will have a new, low field MRI machine (manufactured by Hyperfine) capable of assessing brain volume in place for the 2021 season.
- 2021: A low field MRI machine (manufactured by Hyperfine) capable of assessing brain volume was placed in service in late March 2021. The possibility of randomization was delayed until after the portable MRI became functional.

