5 STUDY ENROLLMENT AND WITHDRAWAL

5.1 Subject Inclusion Criteria

For screening:

- Peripheral *P. falciparum* parasitemia of any density
- Blantyre Coma Score ≤ 2
- No evidence of meningitis on lumbar puncture
- Consciousness not regained after correction of hypoglycemia (if hypoglycemia is present)
- Male or female whose age on the day of screening is between 6 months and 12 years old

If the parents/guardians agree to screening, antimalarial treatment will begin (see Section 6.6), and participants will undergo an ocular funduscopic examination and a brain MRI scan.

Inclusion criteria for randomization:

- Severely increased brain volume on MRI: brain volume score ≥ 6 (see Section 8.2.2.2 for details)
- Willingness to return for follow up visits 1, 6- and 12-months post-randomization

If these criteria are met, guardians will be approached for possible enrollment by a dedicated study nurse or clinician, speaking in the local language (Chichewa).

Antimalarial therapy (standard-of-care) will have already been initiated prior to either of these consent processes

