5.3 Treatment Assignment Procedures

5.3.1 Randomization Procedures

The study will be randomized, but not blinded. Participants will be randomized after completing the eligibility screening procedures. A block randomization scheme will be used to ensure groups of equal size. Blocks sizes of six and nine will be rotated to decrease the predictability of group allocation within a block for data collectors. Children with retinopathy-positive CM will be randomized separately from those with retinopathy-negative CM.

Randomization is based on obtaining a consensus interpretation of brain volume per MRI. If this is not possible for any reason, study participants will be screened but not randomized, and will remain on the PRW. All other study procedures will be followed as described in this protocol.

Randomization is predicated on the risks and benefits as described in this protocol. Endotracheal intubation is required for participants randomized to the “intubation + mechanical ventilation” arm. The current coronavirus pandemic affects the risk/benefit ratio of this arm of the study because endotracheal intubation increases the risk of aerosol spread of the coronavirus (US CDC COVID19 guidance, 4.4.20, www.cdc.gov/coronavirus/2019-ncov/hcp/guidance-risk-assesment-hcp.html). Randomization to the mechanical ventilation arm will be adjusted in accordance with local IRB recommendations during the coronavirus pandemic.

All possible blocks with balanced combinations of group assignment will be documented. Next computer-generated random numbers will be used to select from the balanced blocks. Assignment of study subjects to randomization arm will be performed electronically, through the online data capture mechanism. If Internet service is unavailable at the time of randomization, back up sequentially numbered opaque sealed envelopes prepared before the trial begins will be available. The envelopes will be stored in a secure location with access limited to key study personnel. After a caregiver provides consent for a patient to participate in the study, study arm assignment will first be attempted electronically. If Internet service is unavailable, study personnel will open the next unopened sequentially numbered envelope to reveal the group assignment and dosing calculation sheet.

A master log of all screened and enrolled subjects will be maintained. A subject is considered randomized upon online assignment or opening the envelope to indicate treatment assignment.

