7 STUDY SCHEDULE

7.1 Screening

Participants admitted to the PRW who meet the following initial inclusion criteria will be approached for consent to further screening.

- Peripheral *P. falciparum* parasitemia of any density
- Blantyre Coma Score ≤ 2
- No evidence of meningitis on lumbar puncture
- Does not regain consciousness after correction of hypoglycemia (if hypoglycemia was present)
- Age between 6 months and 12 years
- Oxygen saturation $\geq 85\%$ on room air
- Capillary refill ≤ 3 seconds and absence of abnormal skin tenting

The decision to approach the parent/guardian for screening will only be made after the participant has been stabilized clinically and anti-malarial therapy commenced. In the context of obtaining informed consent, the wide spectrum of CM disease presentation will be explained and our desire to perform two more exams (a retinal exam and an MRI) to further characterize the child's illness will be presented. The fact that neither of these exams are treatment, but that they might lead to further treatment, will be explained.

If the parent/guardian consents to the screening exams, mydriatic eye drops will be added to the participant's eyes and a direct and indirect ophthalmologic exam will be performed. The participant will be taken to MRI.

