9.2 Methods and Timing for Assessing, Recording, and Analyzing Safety Parameters

9.2.1 Adverse Events

ICH E6 defines an adverse event (AE) as any untoward medical occurrence in a participant or clinical investigation subject exposed to an intervention or a pharmaceutical product regardless of its causal relationship to the study treatment. An AE can therefore be any unfavorable and unintended sign (including an abnormal laboratory finding), symptom, or disease, temporally associated with the use of a medicinal (investigational) product. The occurrence of an AE may come to the attention of study personnel during study visits and interviews of a study participant presenting for medical care, or upon review by a study monitor.

Because the safety profiles of the two study interventions are fairly well-defined, and the patient population is critically ill, only AE considered to be possibly attributed to the study intervention will be collected. These will include AE known to be related to the study interventions and pre-specified in 2.4.1.2 and any other unanticipated AE that in the opinion of the investigator was attributed to study interventions. All AEs occurring while on study will be documented appropriately regardless of relationship. All AEs will be followed to adequate resolution.

Any medical condition present at the time that the participant is screened should be considered as baseline and not reported as an AE. However, if the medical condition deteriorates at any time during the study, it will be recorded as an AE.

All AEs will be graded for severity and relationship to study interventions.

Since mortality is an endpoint, death will not routinely be considered an Adverse Event for study purposes. Only events meeting leading to death, hospitalization or prolongation of hospitalization that are outlined in section 2.4.1.2, or that were unanticipated, but that are considered to be possibly related to the study intervention will be reported as SAE.

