14.4 Detailed Informed Consent Process

There are two consent processes potentially involved in this study:

1. Consent for screening. This is the first step for all patients, and the ONLY step for patients who do not have increased brain volume on MRI. These study participants will spend the first 24 hours on the PICU or the PRW (for continuous monitoring for HRV) and if in the PICU will then be moved to the PRW unless they deteriorate, clinically, and warrant ICU care.
2. Consent to enroll in the interventional clinical trial. This option is for patients with MRI evidence of increased brain volume on MRI

In all cases the pertinent material will be supplied in both oral and written form. Forms will be available in English and the local language, Chichewa. The caregiver will be supplied with a copy of the consent form and given ample time to ask questions regarding specifics of the study. A study clinician or study nurse will review the study consent with the parents or guardians accompanying the child. If the parent/guardian is illiterate, the consent will be explained verbally. If the parent/guardian is unable to form a signature, a thumb print will be obtained instead.

Although all subjects will be minors under the age of twelve, the subjects will not be capable of providing assent to participate because all will be, by definition, comatose.

Exclusion of Women, Minorities, and Children (Special Populations)

The major burden of malaria is borne by children; therefore, only children under the age of thirteen years will be enrolled in this study. Subjects will all be Malawian children. All children will be cared for on specially adapted pediatric wards. Parents/guardians are allowed to remain with the children throughout their hospitalization, and all meals and medications are provided without cost. The licensed clinicians providing care are all trained in the management of children with CM, and each research unit is amply staffed with trained dedicated nursing staff. No participant will be excluded on the basis of sex/gender or ethnicity.

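### SAE reporting opens at randomisation, so serious harm from procedures done earlier under screening consent falls outside the stated window, and children never randomised have no window

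*Combined protocol and SAP*

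**What the plan says.** **The window.** Section 9.3.1: "The reporting period for SAEs will be between the time of randomization and the twelve month" visit. Its one extension runs after the study is complete and concerns study product only. Section 5.3.1 fixes the starting moment: "A subject is considered randomized upon online assignment or opening the envelope to indicate treatment assignment".

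**What comes first.** Section 14.4 describes two consents. Of the screening consent it says: "This is the first step for all patients, and the ONLY step for patients who do not have increased brain volume on MRI". Once that consent is given, Section 5.1 says "participants will undergo an ocular funduscopic examination and a brain MRI scan". Section 7.1 presents this to guardians as "our desire to perform two more exams (a retinal exam and an MRI) to further characterize the child's illness", makes clear that neither exam is treatment, and adds mydriatic drops. Appendix A puts the screening code S against the retinal exam, MRI and NIRS. Section 8.3.5 describes the muscle part of NIRS as including a 3-minute cuff inflation on the lower limb.

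**Which events are reported.** Section 9.3.1 also says that "SAEs thought to be related to study related procedures will be reported within 24 hours of their recognition". Section 9.2.1 sets the AE baseline: "Any medical condition present at the time that the participant is screened should be considered as baseline and not reported as an AE".

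**Who stays in the study.** Section 4 keeps screened children without increased brain volume as contributors to Secondary Objectives 2 and 4. It also names screened, non-randomised children in the population for the ventilation safety objective. Section 5.3.1 keeps children on the other study procedures when no consensus MRI reading can be had.

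**The concern.** Section 9.3.1 undertakes to report SAEs linked to study procedures, but its window opens only after the first of those procedures is finished. The AE baseline is set at screening, whereas SAE reporting starts at randomisation. The interval between the two has no SAE rule of its own.

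These are research procedures. Section 2.4.2 says that children whose guardians decline can still have usual care on the research ward, without the study-specific investigations. The protocol also sees some risk in them: Section 2.4.1.1 lists mydriatics among the potential risks, and Section 4 makes repeat daily MRI depend on the child being stable enough to be moved.

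At stake is whether the sponsor and both IRBs would reliably hear of a serious event in the pathway that every candidate passes through. The comparison between arms is not affected.

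**Working it through.** **Step 1. Order of events** (Sections 5.1, 5.3.1, 7.1, 7.2, 14.4): screening consent; drops, funduscopy, MRI and, per Appendix A, NIRS; MRI reading; second consent; randomisation; SAE window opens. Everything before randomisation is outside the window. Lumbar puncture is coded A (all children on the ward), so it is not counted as a screening-consent procedure.

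**Step 2. Children who never reach the window.** Inputs are the season counts in Section 4, beginning with 2018: "Fifty-seven participants were recruited, and 8 were randomized".

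| Season | Screened or recruited | Randomised | Never randomised |
|---|---|---|---|
| 2018 | 57 | 8 | 49 (49/57 = 86%) |
| 2019 | 42 | 24 | 18 (18/42 = 43%) |
| 2020 | 48 | 0 | 48 (48/48 = 100%) |

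- 2018-2019: 57 + 42 = 99 screened; 8 + 24 = 32 randomised; 99 − 32 = 67; 67/99 = 68%.
- 2018-2020: 99 + 48 = 147 screened; 32 + 0 = 32 randomised; 147 − 32 = 115; 115/147 = 78%.
- Check: the 32 randomised agree with Section 11.5 (16 VENT + 16 UC).

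For harm from MRI, 68% is the relevant figure. The scanner was out of use in 2020, so those 48 children may have had no screening MRI. Section 2.3 confirms that 57 children had MRI read in the 2018 season. The documents give no screening totals for 2021 or later.

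**Step 3. Would another section catch the event?**

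- *Section 9.2.1* has every AE on study documented, whatever its cause. That is recording, with no recipient or deadline. The same section limits AE collection to events possibly due to the intervention, and SAE reporting to events listed in Section 2.4.1.2 (hypertonic saline) or unanticipated events possibly related to the intervention. The mydriatic entry is in Section 2.4.1.1, which is not referenced.
- *Section 9.2.1.2* defines relatedness by the intervention or study product.
- *Section 9.2.3* restricts grading and reporting in similar terms.
- *Section 9.2.3.1* reports deaths not attributable to malaria, with no start time or named population. Its non-fatal criteria require attribution to an intervention.
- *Section 4* has the independent safety monitors told of all SAEs, again with no start time, and has them judge relatedness to the interventions. It does not cover the sponsor or the IRBs.

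None of these sets a reporting window for the interval before randomisation or for children never randomised.

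**Step 4. Would moving the start date be enough?** No. A non-fatal serious event during a screening MRI, in a child not yet assigned to an intervention, could still be excluded by the relatedness wording in Sections 9.2.1, 9.2.1.2, 9.2.3 and 9.2.3.1.

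**The case against.** The strongest reply is that the safety system is wider than Section 9.3.1. AEs on study are documented, and a baseline condition that worsens is recorded, with baseline set at screening. Non-malarial deaths go to the monitors, the IRBs and the sponsor. The safety monitors hear of all SAEs. None of these duties is tied to randomisation. This stands in part. A reader might infer from Section 9.3.1 that no record of a screening harm would exist; the documents do not support that. They do leave one explicit window contradicted by broader sentences with no start time, and no clear duty to report a non-fatal screening event to the sponsor or IRBs.

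The exposure can also be overdrawn, and these limits stand:

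- Sections 5.1 and 7.1 name only two screening exams. NIRS rests on one Appendix A cell, and the TCD row of that table carries question marks.
- Section 2.4.1.1 rates the mydriatic risk as low.
- A portable scanner came into service in 2021, and Section 4 allows evaluations at the bedside or in the MRI suite, so transport may not apply to every child.
- For a child later randomised, a procedure-related SAE that occurs after randomisation is inside the window.

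Finally, 78% might be read as the share exposed to an unmonitored MRI hazard. It is not: it includes the 2020 season, and both percentages count children outside the window, not events. The documents report no SAE from a screening procedure.

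**Conclusion.** The point holds for the SAE reporting rule as written. Serious procedure-related events between screening consent and randomisation are outside the stated window. For children never randomised the gap covers their whole time in the study: 67 of 99 (68%) in 2018-2019, or 115 of 147 (78%) with 2020 included. The share varies by season. It was 43% in 2019, the first season under the present eligibility rule described in Section 2.3, so 68% should not be taken as a forecast.

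This rests on two readings: that the explicit window in Section 9.3.1 governs over general sentences without a start time, and that the 2018 count of recruited children means children screened. The conclusion does not extend to AE documentation or to deaths not attributable to malaria, which other sections may capture. The intervention-only relatedness wording is part of the same defect.

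**What to change.** - **Section 9.3.1:** start reporting of SAEs related to study procedures at screening consent. Run this to randomisation or, for a child not randomised, to hospital discharge. Keep the present rule from randomisation to 12 months.
- **Sections 9.2.1, 9.2.1.2, 9.2.3 and 9.2.3.1:** let relatedness cover study procedures as well as the interventions and study product, with the same start point.
- **Section 4:** reconcile the duty to notify the safety monitors with the amended Section 9.3.1, and state that screened, non-randomised children are included.
- **Reporting:** tabulate pre-randomisation and non-randomised SAEs separately, so that the safety comparison between arms is unchanged.

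The cost is a wording amendment in these sections and a few more SAE forms each season. No procedure is added, and sample size and the primary analysis are unaffected.
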